## **5.5 Drug Administration**

Treatment will be administered at the outpatient H. Lee Moffitt Cancer Center Infusion Center. The patients will receive combination of high dose methylprednisolone IV and ofatumumab IV infusion for 3 cycles. This regimen will be followed by a combination of lenalidomide and ofatumumab starting on cycle 4-12 of a 28-day cycle in patients with CR, PR or stable disease. Subjects who do not achieve a CR by C12 may continue lenalidomide single agent at their current dose of lenalidomide until disease progression or unacceptable toxicities.

### **5.5.1 High dose methylprednisolone (HDMP)**

HDMP will be administered at 1 gm/m^2 IV over a minimum of 90 minutes daily with ofatumumab infusions 1-8. The patients will be premedicated with cimetidine (or equivalent) 300mg IV, acetaminophen 1000mg orally, and/or diphenhydramine (or equivalent) 50mg po or IV before receiving HDMP. See Section 5.6.1.5 for concomitant antimicrobial prophylactic therapy

### 5.5.2 Ofatumumab

Ofatumumab infusion will be administered immediately after HDMP. Please refer to dosing schema in Section 1 for ofatumumab dosing. Patients will be pre-medicated prior to infusion of HDMP as above on day 1 and before each ofatumumab infusions 2-8 within 30 minutes to 2 hours prior to the treatment. The last four doses of ofatumumab will follow the standard premedication regimen. Pre-medication before each ofatumumab infusion 9-12 must be given within 30 minutes to 2 hours (+ 15 minutes) prior to the treatment:

#### Pre-medication Requirements prior to Ofatumumab Infusions

Infusion #	Acetaminophen (po) or equivalent	Antihistamine (iv or po) diphenhydramine or equivalent	Glucocorticoid (iv) prednisolone or equivalent
9 th	1000 mg	50 mg	50 mg
10 th	1000 mg	50 mg	50 mg
11 th -12 th	1000 mg	50 mg	0 – 50 mg

#### First Infusion of 300 mg Ofatumumab

The first dose administered of ofatumumab in CLL should be 300 mg to minimize infusion reactions. The initial rate of the first infusion of 300 mg ofatumumab (0.3 mg/mL) should be 12 mL/h. If no infusion reactions occur the infusion rate should be increased every 30 minutes, to a maximum of 400 mL/h, according to the following table. If this schedule is followed, the infusion duration will be approximately 4.67 hours.

#### Infusion rate at 1st Ofatumumab infusion (300mg)

Time	mL/hour
0 – 30 minutes	12
31 – 60 minutes	25
61 – 90 minutes	50

Amendment 5 Dated 03/02/2016

---

91 – 120 minutes	100
121 - 150 minutes	200
151 - 180 minutes	300
181+ minutes	400

If an infusion reaction develops, the infusion should be temporarily slowed or interrupted. Upon restart, the infusion rate should be half of the infusion rate at the time the infusion was paused. If, however, the infusion rate was 12 mL/hour before the pause, the infusion should be restarted at 12 mL/hour. Thereafter, the infusion rate may be increased according to the judgment of the investigator, in the manner described in this section.

#### **Subsequent Infusions of Ofatumumab 2000 mg**

If the previous infusion has been completed without grade  $\geq 3$  infusion-associated adverse effects (AEs), the subsequent infusion of the 2000 mg ofatumumab (2 mg/mL) can start at a rate of 25 mL/hour and should be doubled every 30 minutes up to a maximum of 400 mL/h, according to the following table. Duration of the infusion will be approximately 4 hours if this schedule is followed. If the previous infusion has been completed with grade  $\geq 3$  infusion associated AEs, the subsequent infusion should start at a rate of 12 mL/hour according to table “Infusion rate at 1st Ofatumumab infusion (300mg)”

#### **Infusion rate at subsequent ofatumumab infusion**

Time	mL/hour
0 – 30 minutes	25
31 – 60 minutes	50
61 – 90 minutes	100
91 – 120 minutes	200
121+ minutes	400

During infusion the patient should be monitored closely and appropriate measurements should be performed whenever judged necessary. See Section 5.6.1.5 for concomitant antimicrobial prophylactic therapy

#### **5.5.2.1 Ofatumumab Dose Interruptions or Discontinuation**

Liver chemistry stopping and follow-up criteria have been designed to assure subject safety and evaluate liver event etiology.

##### **5.5.2.1.1 Liver Chemistry Stopping Criteria:**

1. ALT > 3xULN and bilirubin  $\geq$  2xULN (>35% direct bilirubin; bilirubin fractionation required)\*
2. ALT > 8xULN
3. ALT  $\geq$  5xULN for more than 2 weeks

\*NOTE: serum bilirubin fractionation should be performed if testing is available. If testing is unavailable and a subject meets the criterion of total bilirubin  $>2.0 \times$  ULN, then the following actions must still be performed.

When any of the liver chemistry stopping criteria is met, do the following:

- Immediately withdraw investigational product
- Report the event to NOVARTIS and Celgene Corporation within 24 hours of learning its occurrence
- All events of ALT  $\geq$  3xULN and bilirubin  $\geq$  2xULN (>35% direct bilirubin), termed 'Hy's Law', must be reported as an SAE.

NOTE: serum bilirubin fractionation should be performed if testing is available. If testing is unavailable, record presence of detectable urinary bilirubin on dipstick, indicating direct bilirubin elevations and suggesting liver injury.

---

- Perform liver event follow up assessments, and monitor the subject until liver chemistries resolve, stabilize, or return to baseline values as described below.
- Withdraw the subject from the study (unless further safety follow up is required) after completion of the liver chemistry monitoring as described below.
- Do not re-challenge with investigational product.

In addition, for criterion 1:

- Make every reasonable attempt to have subjects return to clinic within 24 hours for repeat liver chemistries, liver event follow up assessments (see below), and close monitoring
- A specialist or hepatology consultation is recommended
- Monitor subjects twice weekly until liver chemistries (ALT, AST, alkaline phosphatase, bilirubin) resolve, stabilize or return to within baseline values

For criteria 2 and 3:

- Make every reasonable attempt to have subjects return to clinic within 24-72 hrs for repeat liver chemistries and liver event follow up assessments (see below)
- Monitor subjects weekly until liver chemistries (ALT, AST, alkaline phosphatase, bilirubin) resolve, stabilize or return to within baseline values; criterion 5 subjects should be monitored as frequently as possible.

Subjects with ALT  $\geq 5$ xULN which exhibit a decrease to ALT  $\geq 3$ xULN, but  $< 5$ xULN and bilirubin  $< 2$ xULN without hepatitis symptoms or rash, and who can be monitored weekly for 4 weeks:

- Can continue ofatumumab

---

- Must return weekly for repeat liver chemistries (ALT, AST, alkaline phosphatase, bilirubin) until they resolve, stabilize or return to within baseline
- If at any time these subjects meet the liver chemistry stopping criteria, proceed as described above
- If, after 4 weeks of monitoring, ALT <3xULN and bilirubin <2xULN, monitor subjects twice monthly until liver chemistries normalize or return to within baseline values.

**5.2.2.1.2 Liver Chemistry Follow-up Assessments:**

Make every attempt to carry out the liver event follow up assessments described below:

- Viral hepatitis serology including:
  - Hepatitis A IgM antibody;
  - Hepatitis B surface antigen and Hepatitis B Core Antibody (IgM);
  - Hepatitis C RNA;
  - Cytomegalovirus IgM antibody;
  - Epstein-Barr viral capsid antigen IgM antibody (or if unavailable, obtain heterophile antibody or monospot testing);
  - Hepatitis E IgM antibody (if subject resides outside the US or Canada, or has traveled outside US or Canada in past 3 months);
- Serum creatine phosphokinase (CPK) and lactate dehydrogenase (LDH).
- Fractionate bilirubin, if total bilirubin  $\geq 2$ xULN
- Obtain complete blood count with differential to assess eosinophilia
- Record the appearance or worsening of clinical symptoms of hepatitis or hypersensitivity, such as fatigue, nausea, vomiting, right upper quadrant pain or tenderness, fever rash or eosinophilia as relevant on the AE report form

---

- Record use of concomitant medications, acetaminophen, herbal remedies, other over the counter medications, or putative hepatotoxins, on the concomitant medications report form.
- Record alcohol use on the liver event alcohol intake case report form

The following are required for subjects with ALT  $\geq 3 \times \text{ULN}$  and bilirubin  $\geq 2 \times \text{ULN}$  ( $> 35\%$  direct) but are optional for other abnormal liver chemistries:

- Anti-nuclear antibody, anti-smooth muscle antibody, and Type 1 anti-liver kidney microsomal antibodies.
- Liver imaging (ultrasound, magnetic resonance, or computerized tomography) to evaluate liver disease.

### **5.5.3 Lenalidomide**

If it is determined the subject will continue to stage 2 of the protocol, on day 1 of Cycle 4, the subject will commence taking lenalidomide daily on a continuous basis. Subjects are to continue taking the lenalidomide after day 28 of each cycle until the day 1 visit of the subsequent cycle occurs. The lenalidomide starting dose will be based on baseline calculated creatinine clearance as follows:

---

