## 2 Schedule of Study Assessments \*

Procedure	All visits/assessments may be scheduled $\pm$ 3 business days										
	Screening  <math>\leq</math> 28 days from Baseline (First day drug administration)	Cycle 1	Cycles 2 - 3	Cycle 4 				Cycles 5-12	Lenalidomide Maintenance Therapy	Discontinuation From Protocol Therapy 	Follow- Up Phase
	Days 1, 8, 15, and 22	Days 1, and 15	Day 1	Day 3 or 4 at investigator discretion	Day 8	Day 15	Day 22	Day 1 and 15			
Study drug administration **		X	X	X					X	X	
Record prior medications, treatments	X										
Record prior anti-cancer therapies	X										
Physical examination, vital signs, weight	X	X 	X 	X 					X 		
ECOG performance status	X	X 	X 	X 					X 		
ECG	X										
Assess lymphadenopathy, spleen / liver 		X 	X 	X 		X 	X 		X 		
Peripheral blood for , ZAP 70, $\beta$ -2 microglobulin, and IgHV mutational status 	X										
Research samples 	X			X							
Baseline lesion assessment	X			X							
Bone marrow 	X			X					X	X	X 
CT of the neck, chest, abdomen & pelvis 	X			X					X		X 
Hematology 	X	X	X	X 		X 	X 	X 	X 	X 	
Serum chemistry 	X	X	X	X 	X 	X 	X 	X 	X 	X 	
Hepatitis B and C serology, HBV DNA PCR 	X 										
Pregnancy testing 	X			X		X	X	X	X		
Register patient into REMS® program	X										

Prescribe lenalidomide via REMS 				X				X			
Record adverse events 		X	X	X				X	X 		
Record concomitant therapies/procedures		X	X	X				X			
Obtain Follow-Up anti-cancer treatments											X
Obtain Follow-Up survival information											X

\* An unscheduled visit can occur at any time during the study. Source must be maintained for these unscheduled visits. The date for the visit and any data generated must be recorded on the appropriate CRF. Source documents for these unscheduled visits must also be maintained.

\*\* See Table 1 for detailed study drug administration schedule.

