 Physical examination of lymphadenopathy, the spleen and liver will be performed on Days 1 and 15 of Cycle 1 to access for tumor flare reaction, and on Day 1 of subsequent cycles to assess response.

 Peripheral blood for ZAP 70 IgVH mutational status, beta-2 microglobulin analyses will be done only at screening. If ZAP 70, IgVH and beta-2 microglobulin was performed within 6 months of screening date, it is not necessary to repeat at screening. Research samples for storage will be drawn during screening, day 1 of cycle 4, day 1 of Maintenance Therapy or discontinuation from protocol therapy if earlier than the end of cycle 12.

 Bone marrow studies will be performed for all subjects at baseline, at the end of cycle 3 (day 21-28 prior to cycle 4), after completion of cycle 12 and every 6 months afterwards during lenalidomide maintenance therapy for two years. Bone marrow studies at any other time point will be performed at the physician's discretion.

 CT of the neck, chest, abdomen & pelvis will be performed at screening, for response assessment at the end of cycle 3 (day 21-28 prior to cycle 4), after the end of cycle 12 (7-10 days after discontinuation of lenalidomide) and every 6 months afterwards during lenalidomide maintenance therapy for two years. After any other time point, CT scans will be performed at the physician's discretion.

 Hematology – CBC with differential WBC and platelet counts. Hematology profiles are required weekly during Cycle 4 (which corresponds to Cycle 1 of lenalidomide-containing therapy), and during any cycle in which the dose of lenalidomide is escalated or re-escalated. For subjects who are on a stable lenalidomide dose (without dose escalation or interruption of the planned dosing schedule) for  $\geq 1$  cycle of treatment, hematology profiles are required on Days 1 and 15 of the cycle.

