### **5.3.2 Exclusion criteria**

1. Any serious medical condition, laboratory abnormality, or psychiatric illness that would prevent the subject from signing the informed consent form.
2. Pregnant or breast feeding females. (Lactating females must agree not to breast feed while taking lenalidomide).
3. Any condition, including the presence of laboratory abnormalities, which places the subject at unacceptable risk if he/she were to participate in the study or confounds the ability to interpret data from the study.
4. Evidence of laboratory TLS by Cairo-Bishop Definition of Tumor Lysis Syndrome (see Appendix H). Subjects may be enrolled upon correction of electrolyte abnormalities.
5. Use of any other experimental drug or therapy within 28 days of baseline.
6. Known hypersensitivity to thalidomide.
7. The development of erythema nodosum if characterized by a desquamating rash while taking thalidomide or similar drugs.
8. Any prior use of lenalidomide.
9. Concurrent use of other anti-cancer agents or treatments.
10. Known seropositive for or active viral infection with human immunodeficiency virus (HIV)
11. Positive serology for hepatitis B (HB) defined as a positive test for HBsAg. In addition, if negative for HBsAg but HBcAb positive and HBsAb negative, a HB DNA test will be performed and if positive the subject will be excluded. Note: If HBcAb positive and HBsAb positive, which is indicative of a past infection, the subject can be included. Patients who are seropositive because of hepatitis B virus vaccine are eligible. Consult with a physician experienced in care &

management of subjects with hepatitis B to manage/treat subjects who are anti-HBc positive

12. Positive serology for hepatitis C (HC) defined as a positive test for HCAb, in which case reflexively perform a HC RIBA immunoblot assay on the same sample to confirm the result
13. Subjects who have current active hepatic or biliary disease (with exception of patients with Gilbert's syndrome, asymptomatic gallstones, liver metastases or stable chronic liver disease per investigator assessment) are ineligible.
14. Chronic or current infectious disease requiring systemic antibiotics, antifungal, or antiviral treatment such as, but not limited to, chronic renal infection, chronic chest infection with bronchiectasis, tuberculosis and active Hepatitis C.
15. History of significant cerebrovascular disease in the past 6 months or ongoing event with active symptoms or sequelae

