#### **Lenalidomide Starting Dose (Cycle 4) Based on Renal Function Prior to Cycle 4 of Treatment**

---

Baseline Calculated Creatinine Clearance (by Cockcroft-Gault)	Starting Lenalidomide Dose
$\geq 60 \text{ ml/min}$	10mg daily on Days 1-28 of each 28-day cycle
$\geq 30 \text{ and } < 60 \text{ ml/min}$	5mg daily on Days 1-28 of each 28-day cycle

At investigator discretion, subjects who have a CrCl between 30-60ml/min may have their lenalidomide dose increased from 5mg to 10mg at the start of cycle 5 or at the start  
Amendment 5 Dated 03/02/2016

---

of subsequent treatment cycles, if they tolerated the prior treatment cycle without requiring dose modifications, interruptions or delays due to toxicity. The maximum allowable target dose for all study subjects is 10 mg daily on Days 1-28 of each 28-day cycle.

Dosing should be at approximately the same time each day but the time of day may be determined per patient to manage any side effects. Only enough lenalidomide for one cycle of therapy will be supplied to the patient each cycle. Prescriptions must be filled within 7 days. If a dose of lenalidomide is missed, it should be taken as soon as possible on the same day. If it is missed for the entire day, it should not be made up. Patients who take more than the prescribed dose of lenalidomide should be instructed to seek emergency medical care if needed and contact study staff immediately.

Subjects experiencing adverse events may need study treatment modifications (See section 5.5).

See Section 5.6.1.1 for allopurinol and oral hydration requirements as prophylaxis against tumor lysis syndrome (TLS).

See Section 5.6.1.2 for prophylactic anti-coagulation.

See Section 5.6.1.5 for concomitant antimicrobial prophylactic therapy

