## **7 Response Criteria**

Baseline lesion assessments must occur within ≤ 28 days of protocol therapy initiation or as indicated in Section 2, Schedule of Study Assessments.

Efficacy assessments will be performed as delineated in Section 2, Schedule of Study Assessments Table.

Assessment for response will be made following the NCIWG 2008 CLL criteria for response (See Appendix F: NCIWG 2008 CLL Criteria for Response).

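### Section 5.5.3 names two different creatinine clearance values as the basis for the Cycle 4 lenalidomide starting dose

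*Combined protocol and SAP*

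**What the plan says.** All references are to the combined protocol and SAP.

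- **Operative sentence, Section 5.5.3:** "The lenalidomide starting dose will be based on baseline calculated creatinine clearance as follows". The column header of the table below it also says *baseline*.
- **Table title, same section:** "Based on Renal Function Prior to Cycle 4 of Treatment".
- **Doses in that table:** CrCl of 60 ml/min or more gives 10 mg daily. CrCl from 30 to below 60 gives 5 mg daily. Both are for days 1-28.
- **Step-up, same section:** a patient with CrCl 30-60 may go from 5 mg to 10 mg from Cycle 5, at the investigator's discretion, "if they tolerated the prior treatment cycle without requiring dose modifications, interruptions or delays due to toxicity".
- **Synopsis:** Table 1 refers to CrCl without a time point. The dosing-schema footnote gives 10 mg only above 60 ml/min and 5 mg for 30-60.
- **Baseline elsewhere:** the screening column of the Schedule of Study Assessments counts "28 days from Baseline (First day drug administration". Exclusion criterion 5 bars "Use of any other experimental drug or therapy within 28 days of baseline". Section 7 says "Baseline lesion assessments must occur within ≤ 28 days of protocol therapy initiation". Schedule footnote 3 treats baseline and the end of cycle 3 as separate times: "Bone marrow studies will be performed for all subjects at baseline, at the end of cycle 3".
- **A lenalidomide clock:** Schedule footnote 5 says of Cycle 4, "which corresponds to Cycle 1 of lenalidomide-containing therapy".

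**The concern.** One dosing rule names two measurements. A site that takes *baseline* in the sense used elsewhere in the protocol would use the CrCl from study start. A site that follows the table title would use a value from shortly before lenalidomide begins. The two agree unless the patient has crossed 60 ml/min in between.

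The more consequential direction is a fall below 60. Section 5.2.1.2 says that about two-thirds of the drug leaves unchanged in the urine in healthy volunteers, and Section 5.5.3 has patients with reduced clearance tolerate a cycle at 5 mg before 10 mg is allowed. The literal reading starts such a patient at 10 mg and omits that step. In the other direction, a patient who has risen to 60 or above starts at 5 mg.

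No later rule looks at CrCl again. The conditions for starting a new lenalidomide cycle (5.5.3.5) and the dose-modification table (5.5.3.6) act on blood counts, tumor lysis and other toxicity.

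**Working it through.** **The plan's own timing.** Table 1 places Cycle 4 Day 1 in week 13. Three cycles of 28 days are 3 × 28 = 84 days = 12 weeks, so Cycle 4 opens week 13. This reproduces.

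**Gap between the two values.** With Cycle 1 Day 1 as study day 1, Cycle 3 Day 15 is day 71 and Cycle 4 Day 1 is nominally day 85. Cycle 3 Day 15 is the last scheduled creatinine if lenalidomide is prescribed 5 to 7 days ahead, as Schedule footnote 11 suggests. Footnote 13 lets Cycle 4 start up to 14 days after the cycle 3 marrow. With the marrow on Cycle 3 Day 28 (day 84), the latest start is day 84 + 14 = 98. A screening value may be 28 days older than Day 1.

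| Later value taken at | From Cycle 1 Day 1 | From screening, 28 days earlier |
|---|---|---|
| Cycle 3 Day 15 (day 71) | 71 − 1 = 70 days (10 weeks) | 70 + 28 = 98 days |
| Nominal Cycle 4 start (day 85) | 85 − 1 = 84 days | 84 + 28 = 112 days |
| Latest Cycle 4 start (day 98) | 98 − 1 = 97 days | 97 + 28 = 125 days |

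The visit window of ±3 business days is left out. The lower two rows run to the start of dosing. The first row is the shorter gap between scheduled measurements, so 10 weeks or more is the fair description.

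**Dose by reading.**

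| CrCl at study start | CrCl before Cycle 4 | Literal reading | Title reading |
|---|---|---|---|
| 60 or more | below 60, at least 30 | 10 mg | 5 mg |
| below 60, at least 30 | 60 or more | 5 mg | 10 mg |
| no crossing | no crossing | same | same |

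Over Cycle 4 the difference is 28 × 10 = 280 mg against 28 × 5 = 140 mg. Because 10 mg is allowed from Cycle 5 if 5 mg was tolerated, the difference can end after one cycle.

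**How small a change crosses the line.** Appendix C (Cockcroft-Gault, men): CrCl = (140 − age) × weight / (72 × creatinine). At fixed age and weight, going from 65 to 60 takes a creatinine rise of 65/60 − 1 = 8.3%. As an illustration, take a man of 72 (the median age at diagnosis in the synopsis). The weight of 80 kg and both creatinine values are assumptions:

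- creatinine 1.2 mg/dL: 68 × 80 / (72 × 1.2) = 63.0 ml/min, so 10 mg;
- creatinine 1.3 mg/dL: 68 × 80 / (72 × 1.3) = 58.1 ml/min, so 5 mg.

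**What 10 mg means below 60.** Assume that two-thirds of clearance is renal and that this part is proportional to CrCl. The AUC of 10 mg, relative to 10 mg at CrCl 60 (which the table permits), is then 1 / (1/3 + 2/3 × CrCl/60):

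| CrCl (ml/min) | 59 | 55 | 50 | 40 | 30 |
|---|---|---|---|---|---|
| Relative AUC | 1.01 | 1.06 | 1.13 | 1.29 | 1.50 |

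**The boundary.** At exactly 60 ml/min the synopsis footnote gives 5 mg and the Section 5.5.3 table gives 10 mg. This mismatch exists whichever reading of *baseline* is meant.

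**The case against.** The best reply is that the table settles the matter where it is used. Its title names both the Cycle 4 start and the time of the measurement, and in a section on starting lenalidomide, *baseline* can naturally mean the value before that drug. The protocol restarts its clock for lenalidomide in footnote 5. As far as the Schedule can be read from the extracted text, its row for baseline lesion assessment is marked at screening and again under Cycle 4, as are the marrow and CT rows. So usage elsewhere is not uniform, and none of the other uses of the word concerns lenalidomide dosing.

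This stands as far as intent goes: the title reading is the likelier one. It does not remove the conflict. The operative sentence and the column header both carry the other word, and the only explicit gloss, in the screening header, is the first day of drug administration.

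It is also fair to say that the exposure at issue is one the protocol accepts, since 10 mg at CrCl 30-60 is permitted from Cycle 5. But that permission depends on a tolerated cycle at 5 mg, which the literal reading omits.

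A reader might infer more than the documents support:

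- *That the plan deliberately doses on a value three or four months old.* The title says otherwise.
- *That a crosser gets double the exposure he should.* Two-fold is the ratio of the doses. Compared with a patient at the permitted limit, the excess is slight for small crossings. The larger ratios need a fall to 40 or 30 ml/min, and nothing in the documents says how often that happens. The model is itself rough, because Section 5.2.1.2 describes the excretion as at least partly active.
- *That a compulsory Day 1 recheck overriding the prescribed dose is needed.* That would be a new dosing rule, not a cure for the inconsistency.

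**Conclusion.** The rule is wrong as written, and the issue is minor. Section 5.5.3 contradicts itself on which CrCl sets a first-exposure dose. A literal reading gives the other dose to any patient who crosses 60 ml/min over about 10 weeks or more, and a patient who has fallen below 60 loses the 5 mg tolerance cycle.

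Only crossers are affected. The documents give no distribution of CrCl or of its change, so their number cannot be estimated. Weekly hematology in Cycle 4, weekly chemistry through at least the first two lenalidomide cycles, and the hold rules in 5.5.3.6 limit harm.

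A reader might also infer that the efficacy result is at risk. For the primary endpoint it is not: Sections 1 and 10.1 read response at the end of cycle 3, before lenalidomide starts. Sample size, alpha and power do not depend on this rule.

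The inconsistency and the calendar figures come straight from the text. The exposure ratios rest on the stated clearance assumptions, and the worked patient is an illustration only.

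**What to change.** Make three wording edits:

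1. In the operative sentence of Section 5.5.3, replace *baseline* with *most recent calculated creatinine clearance before Cycle 4 Day 1*.
2. Make the same replacement in the column header of the starting-dose table.
3. In the synopsis dosing-schema footnote, give 10 mg for CrCl ≥60 ml/min and 5 mg for ≥30 to <60 ml/min, to match the table.

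The edits add no procedure, because creatinine is already scheduled through cycle 3. They do not touch the sample size or the analysis. The step-up sentence in 5.5.3 can keep its 30-60 wording without effect, since a patient at exactly 60 already starts on 10 mg under the table.

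A check against the Cycle 4 Day 1 chemistry can be left to the investigator's discretion. Making it compulsory could mean a second prescription within the cycle, with the surveys and shipment described in Schedule footnote 11.
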